### 8.3.1 Non-Hematologic Adverse Events Related to Sunitinib

### Hypertension Management

Specific guidelines for management of this adverse event are provided in the table below. In addition, guidance on the collection and recording of BP information is provided in Appendix VII.

BP measurements – systolic/diastolic Patients not receiving maxima	Treatment/Dose Modification  I antihypertensive therapy:
140-149 mmHg (systolic) OR 90-99 mmHg (diastolic)	
 
Add new or additional antihypertensive meds or increase dose of existing meds
 
Maintain dose of sunitinib
 

150-179 mmHg (systolic) OR	Add new or additional antihypertensive meds or increase dose of existing meds

100-104 mmHg (diastolic)	
 
Hold sunitinib until BP falls to <140/90
 
Decrease sunitinib by 1 dose level if 2 new antihypertensive drugs added to control BP
 
	
≥ 180 mmHg (systolic)  OR  ≥ 105 mmHg (diastolic)	
 
Hold sunitinib until BP controlled
 
Add new or additional antihypertensive meds or increase dose of existing meds
 
Monitor patient closely for hypotension (if on antihypertensive meds) until sunitinib is restarted.
 
Resume sunitinib at the next lower dose level when BP falls to <140/90
 
	
Hypertensive Crisis	

Discontinue sunitinib; Take off study

Hospitalize patient for management

	
modification of antihypertensiv	tihypertensive therapy (four antihypertensives for 2 weeks without dose ve medications): diuretics, beta blocker or central sympathetic blocker, sodilator or calcium channel blocker (CCB)	
> 160 mmHg (systolic) OR > 105 mmHg (diastolic)	
 
Hold sunitinib
 
Maintain antihypertensive meds and monitor patient closely for hypotension until sunitinib is restarted.
 
Resume treatment at one lower dose level when BP falls to <140/90
 
	
Hypertensive Crisis	

Discontinue sunitinib; Take off study

Hospitalize patient for management

	
* Maximal antihypertensive weeks.	therapy is defined as four antihypertensive medications given for 2	

### Oral antihypertensive medications

Agent class	Agent	Initial dose	Intermediate dose	Maximum dose	Hepatic metabolism
Dihydro- pyridine	nifedipine XL	30 mg daily	60 mg daily	90 mg daily	CYP 3A4 substrate
Calcium- Channel Blockers	amlodipine	2.5 mg daily	5 mg daily	10 mg daily	CYP 3A4 substrate
(DHP CCB)	felodipine	2.5 mg daily	5 mg daily	10 mg daily	CYP 3A4 substrate and inhibitor
	metoprolol	25 mg twice daily	50 mg twice daily	100 mg twice daily	CYP 2D6 substrate
Selective	atenolol	25 mg daily	50 mg daily	100 mg daily	No
β Blockers (BB)	acebutolol	100 mg twice daily	200-300 mg twice daily	400 mg twice daily	Yes (CYP450 unknown)
	bisoprolol	2.5 mg daily	5-10 mg daily	20 mg daily	Yes (CYP450 unknown)
Angiotensin Converting	captopril	12.5 mg 3x daily	25 mg 3x daily	50 mg 3x daily	CYP 2D6 substrate
Enzyme	enalapril	5 mg daily	10-20 mg daily	40 mg daily	CYP 3A4 substrate

Inhibitors (ACEIs)	ramipril	2.5 mg daily	5 mg daily	10 mg daily	Yes (CYP450 unknown)
	lisinopril	5 mg daily	10-20 mg daily	40 mg daily	No
	fosinopril	10 mg daily	20 mg daily	40 mg daily	Yes (CYP450 unknown)
	Rarely used: perindopril	4 mg daily	none	8 mg daily	Yes, but not CYP450
	Rarely used: quinapril	10 mg daily	20 mg daily	40 mg daily	No
	losartan	25 mg daily	50 mg daily	100 mg daily	CYP 3A4 substrate
	candesartan	4 mg daily	8-16 mg daily	32 mg daily	CYP 2C9 substrate
Angiotensin II Receptor	irbesartan	75 mg daily	150 mg daily	300 mg daily	CYP 2C9 substrate
Blockers (ARBs)	telmisartan	40 mg daily	none	80 mg daily	Yes, but not CYP450
	valsartan	80 mg daily	none	160 mg daily	Yes, but not CYP450
α and β Blocker	labetolol	100 mg twice daily	200 mg twice daily	400 mg twice daily	CYP 2D6 substrate and inhibitor

Agents in **bold characters** are suggested as optimal choices to avoid or minimize potential drug-interactions with sunitinib through CYP450

### 8.3.2Management of Paroxysmal Hypertension

All patients must have adequate blood pressure control before entry into the trial. This includes persistent hypertension as well as episodic paroxysmal hypertension. If the patient experiences paroxysmal hypertension or symptoms thereof during the trial, the patient will cease sunitinib until blood pressure is controlled. The investigators will then ensure that the patient has not progressed. Subsequently, management will be as follows;

1) Gradual titration with a calcium entry blocker (Norvasc) (amlodipine) starting with 5 mg/day for a total of 20 mg/day. The aim will be to keep BP at less than 150/90 mm.

If the above alone is insufficient at maximal doses, consideration will be given to the addition of one of the following agents:

- 2) The mixed alpha/beta receptor blocker labetolol at 200 mg twice daily up to a maximum of 400 mg twice daily.
- 3) The alpha 1 receptor blocker doxazosin (Prazosin) 2 mg up to a maximum of 16 mg/day will be considered for refractory cases.

Should the patient's blood pressure fail to be controlled by these measures, or whose overall condition deteriorates due to uncontrolled hypertension will be discontinued from the protocol and treated with ongoing best supportive care.

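### Section 8.3.2 takes amlodipine to 20 mg/day before the next agent is considered, twice the 10 mg daily maximum in the protocol's own drug table, with no stated exception

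*Combined protocol and SAP*

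**What the plan says.** Section 8.3.2 (Management of Paroxysmal Hypertension) applies when a patient has paroxysmal hypertension, or symptoms of it, during the trial. Its first instruction concerns the study drug: "the patient will cease sunitinib until blood pressure is controlled". The investigators then check that the disease has not progressed, and antihypertensive treatment follows in steps.

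- Step 1 is amlodipine: "Gradual titration with a calcium entry blocker (Norvasc) (amlodipine) starting with 5 mg/day for a total of 20 mg/day". The target is given with it: "The aim will be to keep BP at less than 150/90 mm".
- The move to the next agent is conditional: "If the above alone is insufficient at maximal doses, consideration will be given to the addition of one of the following agents".
- Step 2 is "labetolol at 200 mg twice daily up to a maximum of 400 mg twice daily". Step 3, for refractory cases, is doxazosin from 2 mg to at most 16 mg/day.
- A patient should leave the protocol for best supportive care should "blood pressure fail to be controlled by these measures", or if uncontrolled hypertension worsens the patient's overall condition.

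The table headed Oral antihypertensive medications stands just before 8.3.2, at the end of the hypertension guidance in 8.3.1. It has columns for initial, intermediate and maximum dose. Amlodipine is listed at 2.5 mg, 5 mg and 10 mg daily. Labetalol is listed at 100 mg twice daily, then "200 mg twice daily", then a maximum of "400 mg twice daily". Doxazosin is not in the table.

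**The concern.** The protocol gives two maximum doses for the same drug, and the section written for the event prints the higher one. A site treating a paroxysmal episode from 8.3.2 may go to 20 mg/day. A site that reads the maximal dose from the drug table stops at 10 mg/day. Both can claim to be following the protocol.

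The ceiling has consequences inside 8.3.2. It fixes the point at which labetalol or doxazosin is considered. Amlodipine at full dose is also the first of the measures whose failure leads to discontinuation. Such episodes are foreseeable: section 2.0 describes catecholamine-secreting tumours, and section 8.3 names hypertension among the main toxic effects that may limit the sunitinib dose. A dose ceiling in a safety algorithm should be one figure.

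**Working it through.** The check compares stated doses. No sample-size or power formula is involved.

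**Inputs.** Section 8.3.2 supplies the start dose and ceiling for amlodipine and labetalol. The oral antihypertensive table supplies the initial, intermediate and maximum doses.

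| Drug and dose | Section 8.3.2 | Drug table | Ratio |
|---|---|---|---|
| Amlodipine, ceiling vs maximum | 20 mg/day | 10 mg daily | 20/10 = 2.0 |
| Labetalol, ceiling vs maximum | 400 mg twice daily | 400 mg twice daily | 400/400 = 1.0 |
| Amlodipine, start vs initial | 5 mg/day | 2.5 mg daily | 5/2.5 = 2.0 |
| Labetalol, start vs initial | 200 mg twice daily | 100 mg twice daily | 200/100 = 2.0 |
| Doxazosin | 2 to 16 mg/day | not listed | cannot be compared |

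**Step 1: is 20 mg/day a ceiling?** The phrase giving the total is loose. But the sentence starts at 5 mg/day and titrates gradually, and the next sentence but one refers to maximal doses. The natural reading is a daily ceiling of 20 mg.

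**Step 2: does it exceed the table?** Yes, by a factor of 2.0. The higher start doses do not breach a maximum, because 5 mg and 200 mg twice daily are the table's intermediate doses. The amlodipine ceiling does breach one.

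**Step 3: is there a stated exception?** Neither 8.3.2 nor the table gives a higher amlodipine maximum for paroxysmal episodes, says that 8.3.2 overrides the table, or explains the difference. Amlodipine appears elsewhere only in the Appendix VI lists of CYP3A4 substrates and inhibitors, which give no dose.

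**Step 4: what changes with the ceiling?** Under 8.3.2 as written, the next agent is considered when 20 mg/day has proved insufficient. With the table maximum, it would be considered at 10 mg/day. The two readings part over the range from 10 to 20 mg/day.

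**The case against.** The best defence is scope. The table sits in 8.3.1, which deals with adverse events related to sunitinib, while 8.3.2 is a separate section for paroxysmal episodes. The table does not say that its maxima bind 8.3.2, and its only note concerns preferred agents. Section 8.3.2 also looks like a regimen of its own. Both shared drugs start at twice the table's initial dose, and doxazosin is not in the table. Compared start to initial and ceiling to maximum, only one of the four shared figures agrees (the labetalol maximum).

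This stands in part: a deliberate difference is possible. A reader might infer that 20 mg is a plain slip in a section that otherwise follows the table. The documents do not support that, because the match is not close enough. But the table is headed generally, has a column for maximum dose, and is the only other place where amlodipine is dosed. If a different ceiling was meant, the protocol does not say so.

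The rule in 8.3 that the lowest recommended dose prevails does not settle the matter. It concerns sunitinib adjustments when several adverse events conflict.

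Three stronger readings are tempting and should not be drawn.

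- *That a patient would be on one antihypertensive alone up to 20 mg/day.* Blood pressure must be controlled before entry, and Appendix VII records antihypertensives already in use at that time. Labetalol or doxazosin is the next agent of 8.3.2, not necessarily the patient's second drug.
- *That the 150/90 aim in 8.3.2 contradicts the 140/90 value in 8.3.1.* The first is a target for antihypertensive titration and the second a threshold for restarting sunitinib. Section 5.2.6.4 defines poor control as 150 or higher systolic or 90 or higher diastolic, which agrees with the 8.3.2 aim. So control has a usable meaning there.
- *That the whole 8.3.1 hypertension table should govern paroxysmal episodes.* At 140–149 systolic or 90–99 diastolic that table keeps the sunitinib dose unchanged, and it has no symptom trigger. It would replace the stop that 8.3.2 requires, and it would add off-study and dose-reduction rules that 8.3.2 does not contain.

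**Conclusion.** The inconsistency is real and limited to one figure: an amlodipine ceiling of 20 mg/day in 8.3.2 against 10 mg daily in the drug table, a factor of 2.0, with no exception stated. It sets when the next 8.3.2 agent is considered. It rests on two assumptions: that the total in 8.3.2 is a daily ceiling, and that a generally headed maximum applies unless the protocol says otherwise.

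A reader might go further and infer that 20 mg is unsafe, that 10 mg was certainly intended, or that the trial's result is affected. The documents support none of these. They show no harm from 20 mg, do not say which figure was meant, and do not give the number of patients concerned. Nothing here bears on the rule of three or more responses in 28 patients in section 11.3. This is a dose figure in a safety algorithm that should be corrected because it is unexplained and easily put right.

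**What to change.** In step 1 of 8.3.2, change the amlodipine ceiling to 10 mg/day, and state that labetalol or doxazosin is considered once blood pressure is not controlled at that dose. The 5 mg/day start can stay. If the sponsor does intend 20 mg/day, state it as an exception for paroxysmal hypertension, with the reason, both in 8.3.2 and against the amlodipine row of the table.

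Leave unchanged the instruction in 8.3.2 to stop sunitinib for any paroxysmal episode or its symptoms.

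The cost is one dose figure and its matching wording, or one explained exception in two places, sent through the amendment route of section 15.3. It adds no visits, tests or patients.

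### Section 8.3.2 titrates amlodipine to 20 mg/day, twice the 10 mg daily maximum in the protocol's own antihypertensive table, with no exception stated

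*Combined protocol and SAP*

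**What the plan says.** Two adjacent parts of the treatment plan give doses for amlodipine.

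- **Section 8.3.1, table of oral antihypertensive medications.** The columns are initial, intermediate and maximum dose. The row reads "amlodipine 2.5 mg daily 5 mg daily 10 mg daily". The labetalol row reads "labetolol 100 mg twice daily 200 mg twice daily 400 mg twice daily".
- **Section 8.3.2, paroxysmal hypertension.** Step 1 is gradual titration of amlodipine "starting with 5 mg/day for a total of 20 mg/day", aiming for a blood pressure below 150/90. The route to a further drug opens with "If the above alone is insufficient at maximal doses". Step 2 is "labetolol at 200 mg twice daily up to a maximum of 400 mg twice daily". Step 3, for refractory cases, is an alpha-1 blocker from 2 mg to 16 mg/day, labelled doxazosin with Prazosin in brackets. A patient whose pressure these measures do not control is discontinued from the protocol.

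Section 8.3.2 does not refer to the table, and the table carries no exemption for paroxysmal hypertension.

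**The concern.** One drug has two ceilings in current text, and nothing says which governs. Section 8.3.2 makes the higher ceiling the gateway to the second agent. Followed as written, it escalates a patient who is not controlled at 10 mg/day beyond the protocol's own maximum before any alternative is considered. A prescriber or pharmacist who checks the dose against the table would stop at 10 mg/day.

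The situation is foreseeable. Section 2.0 describes control of hypertension as part of the therapeutic goal in metastatic disease, and Section 8.3 lists hypertension among the toxic effects of sunitinib that may limit dose. What is at stake is safe and uniform care of these patients, not the efficacy inference.

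**Working it through.** There is no derived figure to reproduce; the check is a comparison of stated doses.

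**Inputs**

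| Drug | Source | Start | Ceiling |
|---|---|---|---|
| Amlodipine | 8.3.1 table | 2.5 mg daily (intermediate 5) | 10 mg daily |
| Amlodipine | 8.3.2 step 1 | 5 mg/day | 20 mg/day |
| Labetalol | 8.3.1 table | 100 mg twice daily (intermediate 200) | 400 mg twice daily |
| Labetalol | 8.3.2 step 2 | 200 mg twice daily | 400 mg twice daily |

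**Step 1: amlodipine ceiling.** Ratio 20/10 = 2.0; excess 20 − 10 = 10 mg/day. Both figures are daily totals, so splitting the dose does not reconcile them.

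**Step 2: is the table a fair comparator?** Labetalol is the only other drug in both places. Its ceilings agree: 400/400 = 1.0. Section 8.3.2 starts both drugs at the table's intermediate dose (5/5 = 1.0 and 200/200 = 1.0), so the starting doses stay within the table's range. The amlodipine ceiling does not.

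**Step 3: is there a stated exception or tie-breaker?** Three places could supply one.

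- Section 8.3.2 gives a blood pressure aim but no reason to exceed the table.
- Appendix VI lists amlodipine only as a CYP3A4 substrate and inhibitor, without a dose.
- Section 8.3 resolves conflicting recommendations by taking the lowest level, but that rule governs sunitinib dose adjustments, not antihypertensives.

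**Step 4: order of escalation.** The condition for adding a drug directly follows the 20 mg/day titration, so its maximal dose is most naturally 20 mg/day. If it meant the table's 10 mg, step 1 would contradict the sentence after it. On the literal reading the sequence is 5 mg, then 10 mg (table maximum), then up to 20 mg, then a second agent. The 8.3.1 blood pressure table separately allows additional drugs when pressure is raised, so this ordering belongs to the 8.3.2 ladder only.

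**The case against.** The strongest defence is that Section 8.3.2 is a separate algorithm for a different problem. It has its own pressure aim (below 150/90, against below 140/90 for resuming sunitinib in 8.3.1), its own starting doses, and an alpha-1 blocker that the table does not list. A specific section may depart from a general table on purpose, and it calls for gradual titration to a target, not automatic escalation to 20 mg. This stands in part: a reader might infer that 20 mg/day is a mistake, and the documents do not show that. They also do not show that it is deliberate. A departure that doubles a stated maximum needs to be declared, and it is not.

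Three other stronger readings go too far.

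- **That no justification exists anywhere.** Part of the Section 2.0 background was not in the text available for review, so the statement holds only for the text that was.
- **That sunitinib's status during titration is undefined.** The section says "the patient will cease sunitinib until blood pressure is controlled" and then "Subsequently, management will be as follows". The second phrase is loose, but the natural reading is that the drug is held until control is reached.
- **That monitoring is absent.** Section 8.3.2 has no hypotension instruction of its own, but 8.3.1 has one in its row for 180/105 or above ("Monitor patient closely for hypotension (if on antihypertensive meds) until sunitinib is restarted") and a similar one for patients above 160/105 on maximal therapy. Sections 8.2 and 9.1 add repeat checks for rising pressure, and Section 9.1 allows more frequent measurement at the physician's discretion. The gap matters only if the higher ceiling is kept.

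**Conclusion.** The inconsistency is real: 20 mg/day in Section 8.3.2 against a 10 mg daily maximum in the 8.3.1 table, a factor of two, with no exception stated in the text available for review. It should be corrected because it sits in a dosing rule that bears on patient safety and because, read literally, the higher dose comes before the second agent.

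The scope is limited. Only patients with paroxysmal hypertension not controlled at 10 mg/day are affected. The documents give no frequency for them, in a trial of up to 28 response-evaluable patients. Type I error, power and sample size do not depend on it. The conclusion rests on reading the table's maximum column as a ceiling that applies throughout the protocol unless otherwise stated, which the agreement for labetalol supports but does not prove.

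**What to change.** In Section 8.3.2 step 1, set the amlodipine ceiling to 10 mg/day, so that this figure defines the maximal dose that opens the way to a second agent. The documents alone do not settle which figure was intended, so the clinical and pharmacy team should confirm it. If they intend 20 mg/day, Section 8.3.2 should say that it is an exception to the table, give the reason, and carry over the 8.3.1 instruction to monitor closely for hypotension. In the same edit, name the single alpha-1 blocker meant in step 3, which now puts two drug names over one dose range.

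The amendment needs no extra patients or data, but the lower ceiling has clinical costs:

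- Some patients would receive a second agent earlier.
- The ladder before discontinuation for uncontrolled pressure becomes shorter.
- Where the 150–179/100–104 row of 8.3.1 applies, sunitinib drops one level if two new antihypertensives are added, so a reduction could come sooner. Section 8.3 bars re-escalation after a reduction for confirmed toxicity, apart from the QTc provision.

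The team should weigh these costs when choosing between the two ceilings.

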### 8.3.3 Hematological toxicity

The following table outlines when dose adjustments are required for haematological toxicity

Event	AE Grade	Dose modification
	or	
	Observation	
	Grades 1 and 2	Maintain dose
	Grade 3 * ‡	Hold sunitinib until $\leq$ grade 2, then resume at same
Neutropenia †		dose level
_	Grade 4 *	Hold sunitinib until $\leq$ grade 2, then reduce 1 dose
		level and resume treatment
	Grades 1 and 2	Maintain dose
	Grade 3 * ‡	Hold sunitinib until $\leq$ grade 2, then resume at same
Thrombocytopenia †		dose level
	Grade 4 *	Hold sunitinib until $\leq$ grade 2, then reduce 1 dose
		level and resume treatment

† Must be documented on 2 separate occasions at least 24 hours apart.

### 8.3.4 Other Non-Hematologic Adverse Events

Event	AE Grade	Dose modification
	or	
	Observation	
Fever, chills, flu-like	Grades 1-4	Maintain dose
symptoms		
	Grades 1 and 2	Maintain dose
Fatigue (lethargy,	Grade 3 *	Hold sunitinib until $\leq$ grade 2, then reduce 1 dose
		level and resume treatment
malaise, asthenia)	Grade 4	Hold sunitinib until $\leq$ grade 2, then reduce 1 dose
		level and resume treatment
	>450 but	Review patient's concomitant medications for
	< 550 msec	QT interval-prolonging agents. Correct any
		electrolyte abnormalities.
		Continue sunitinib at current dose level.

\* If neutrophil and/or platelet counts have not recovered to baseline or better within 3 weeks of dose interruption, the patient is withdrawn from the study \* Recurrent grade 3 events require dose reduction.

QTc Prolongation	≥ 550 msec	Stop sunitinib and any other QT-interval prolonging agents immediately. Correct any electrolyte abnormalities, then  1. If there is a plausible explanation for AE other than sunitinib treatment, resume sunitinib at current dose level.  2. If sunitinib may have contributed to the AE:  Reduce 2 dose levels and restart sunitinib.  If QTc remains <500 msec after 14 days at reduced dose, increase one dose level and continue sunitinib.  If QTc remains <500 msec after 14 days, original
		dose of sunitinib may be resumed.
	Grades 1 and 2	Maintain dose
	Grade 3 *	Hold sunitinib until $\leq$ grade 1, then resume
Hand-foot syndrome		treatment at same dose or reduce 1 dose level
	Grade 4	Hold sunitinib until $\leq$ grade 1, then reduce 1 dose
		level or discontinue treatment
	Grades 1-2	Maintain dose *
AST and/or ALT	Grades 3-4	Sunitinib held until ≤grade 2,then resume at dose
elevation		level-1. If grade 3-4 recurs a 2 nd time, discontinue
(SGOT, SGPT)		sunitinib. Also discontinued if there is no resolution
		to < grade 2 on first episode.
Posterior Reversible	Any occurrence	Cease sunitinib and await recovery with
Encephalopathy Syndrome		symptomatic management. Discontinue treatment.
CPK elevation	Grade 2	Hold sunitinib until ≤ grade 2, then reduce 1 dose level and resume treatment

\* Recurrent grade 3 events require dose reduction.

- Patients requiring a delay of > 4 weeks or > 3 dose reductions should go off protocol therapy but may remain at the principal investigators discretion
- 24-48 hrs are suggested as elapse time between decision steps suggested in the algorithm unless persistent severe hypertension occurred.
- Hypertension should be graded according to NCI CTCAE Version 3.0 and recorded on CRFs.
- While patients are receiving treatment with sunitinib, the early initiation of antihypertensive treatment for grade 1 or 2 hypertension to minimize more severe or persistent hypertension is not considered a grade 3 adverse event.
- Decisions to hold or decrease the sunitinib dose during treatment must be based on BP readings taken in the clinic by a medical professional.

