#### Sunitinib dose levels\*

Dose Level	Daily Dose
-3	12.5 mg
-2	25 mg
-1	37.5 mg
0	50 mg

\* dispensed using 12.5mg, 25mg and 50mg capsules as applicable

The major toxic effects of sunitinib which may limit dose are: neutropenia, thrombocytopenia, fatigue, hand-foot syndrome, hypertension, and changes in liver enzymes. The guidelines that follow outline dose adjustments for several of these toxic effects. If a patient experiences several adverse events and there are conflicting recommendations, please use the recommended dose adjustment that reduces the dose to the lowest level.

For all dose modifications, please note:

- Cycle length of 6 weeks should be maintained even if doses are missed during the 4 weeks of planned treatment (i.e. treatment interruptions should not re-set the cycle timing such that the next cycle starts earlier and missed doses should not be 'made up' in the observation period during weeks 5 and 6). However, the cycle length may be increased in the event that a new cycle of treatment is delayed.
- Supportive care recommendations for sunitinib-related effects can be found in section 8.1.3.
- Patients requiring more than three dose reductions will be removed from protocol therapy.
- Patients who do not recover from toxic effects as required within 3 weeks will be removed from protocol therapy.
- No dose escalations are permitted after reductions for confirmed toxicity (except for the circumstance as described for QTc prolongation in section 8.3).

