### Discontinue sunitinib if:

- after holding study drug for 2 weeks, the repeat MUGA has not improved to normal or to the levels that allow continuing treatment
- after holding study drug, and restarting it, the LVEF falls again into the "hold" range IF LVEF remains at a "Continue And repeat MUGA" or improves from a HOLD to a "Continue And repeat MUGA" category, additional MUGA scans prior to the next scheduled MUGA will be at the discretion of the investigator.

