### 8.3.5 Other Hematologic and Non-hematologic Adverse Events (not specifically addressed above)

**General Management Guidelines** 

General Managem	ent Guidennes
Observation	Action
AE resolves promptly* with supportive care	Maintain dose level

 
Grade 3 or higher (non-haematological) AE related to sunitinib and lasting >5 days that does not resolve to grade 2 or below despite maximum supportive care for ≤ 48 hours.
 
Lower grade but related AEs (e.g., creatinine)
 
	Reduce one dose level
AE does not resolve to grade 2 or below after treating patient at the lowest ( i.e. , 25 mg daily) reduced dose level.	In general, remove patient from study

\*Prompt resolution indicates resolution to grade 2 or below.

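### The asterisk footnote to the 8.3.3 haematological table sets recovery at baseline within 3 weeks, while the grade 3-4 rows it qualifies resume treatment at grade 2 or better

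*Combined protocol and SAP*

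**What the plan says.** The table in section 8.3.3 treats neutropenia and thrombocytopenia alike. At grades 1 and 2 the instruction is "Maintain dose". The two grade 3 rows hold sunitinib until toxicity is no worse than "grade 2, then resume at same" dose level. The two grade 4 rows hold to the same point: "grade 2, then reduce 1 dose" level and restart. All four carry an asterisk. The asterisk footnote says that if neutrophil or platelet counts "have not recovered to baseline or better within 3 weeks of dose interruption, the patient is withdrawn from the study". The PDF layout prints this footnote inside the 8.3.4 table, but it names these two counts and its mark matches the 8.3.3 rows, so it belongs to 8.3.3.

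Other stopping rules in section 8.3 bear on the point:

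- The general notes under the dose-level table say "Patients who do not recover from toxic effects as required within 3 weeks will be removed from protocol therapy".
- The LVEF rule discontinues sunitinib if "after holding study drug for 2 weeks, the repeat MUGA has not improved to normal or to the levels that allow continuing treatment".
- The AST/ALT row in 8.3.4 restarts at grade 2 or better, but discontinues if a first episode does not resolve to better than grade 2.
- Section 8.3.5, for events not covered elsewhere, states "Prompt resolution indicates resolution to grade 2 or below" and in general removes a patient who does not reach that level at the lowest dose.
- A closing bullet in 8.3.4 takes patients off protocol therapy after a delay of more than 4 weeks, but lets the principal investigator keep them on.

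**The concern.** The rows and their own footnote use different recovery levels for the same event. A site that follows the footnote would withdraw a patient whose counts the same table accepts for dosing. A site that follows the rows would keep treating that patient.

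The rule is likely to be used. The dose-adjustment notes say "The major toxic effects of sunitinib which may limit dose are: neutropenia, thrombocytopenia", ahead of the other effects listed. Three centres are named in section 5.0, so identical counts could lead to different decisions. At stake are how long some patients stay on sunitinib and whether discontinuations for haematological toxicity mean the same thing at each site. The second matters for the toxicity objective (1.2).

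**Working it through.** The plan states no figure on this point, so there is none to reproduce. The check sets the rules side by side.

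| Rule | Level that permits treatment | Level below which the patient stops | Time limit | Consequence |
|---|---|---|---|---|
| 8.3.3, four grade 3-4 rows | grade 2 or better | not given in the row | none in the row | resume |
| 8.3.3, asterisk footnote | not given | baseline | 3 weeks from interruption | withdrawn from study |
| 8.3, general note | not given | whatever is required elsewhere | 3 weeks | off protocol therapy |
| LVEF rule | normal, or a level that allows continuing | the same | 2-week hold | sunitinib discontinued |
| 8.3.4, AST/ALT row | grade 2 or better | better than grade 2 (first episode) | none | sunitinib discontinued |
| 8.3.5 | grade 2 or better | grade 2, at the lowest dose | none | generally removed |
| 8.3.4, closing bullet | not given | not given | delay over 4 weeks | off therapy, unless the principal investigator decides otherwise |

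**Row counts.** Of the 4 grade 3-4 rows in 8.3.3, 4 resume at grade 2 or better and 0 name baseline. The graded hold rows in 8.3.3 and 8.3.4 number 2 (neutropenia) + 2 (thrombocytopenia) + 2 (fatigue) + 2 (hand-foot) + 1 (AST/ALT) + 1 (CPK) = 10. Of these, 8 restart at grade 2 or better, 2 (hand-foot) at grade 1 or better, and 0 at baseline. The CPK row holds at grade 2 until grade 2 or better, which is met at onset, so it says little about restart levels. Without it the count is 7 of 9.

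**Test cases on the literal text.**

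1. A patient reaches grade 2 on day 21 of a hold. The row says resume. The count is below baseline at 3 weeks, so the footnote says withdraw.
2. A patient reaches grade 2 and resumes on day 10, and on day 21 after the interruption is at grade 1 but below baseline. The table says to continue at that grade. The footnote counts from the interruption and says withdraw.

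**Can a patient lie between the two levels?** Section 5.1.7 requires normal marrow function, and 5.1.10 requires granulocytes above 1.5 and platelets above 100 x 10^9/L. Appendix IV points to CTCAE version 3.0 without printing grade limits, so the lower limit of grade 2 is an assumption here. The minimum gap is the entry limit minus that lower limit.

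- Granulocytes, assumed limit 1.0 (range 0.75 to 1.25): 1.5 - 1.0 = 0.5 (range 0.75 down to 0.25) x 10^9/L.
- Platelets, assumed limit 50 (range 25 to 75): 100 - 50 = 50 (range 75 down to 25) x 10^9/L.

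The gap is positive for any grade 2 lower limit below the entry limit, and wider for patients who start well above the entry minimum. These figures show only that the conflict can occur. They do not show how often.

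**The case against.** **Likely intent.** The strongest defence is that the footnote caps the length of a hold, so a patient who reaches grade 2 within 3 weeks simply resumes and the footnote no longer applies. The literal alternative is odd: in test case 2 the patient would have to climb back to baseline while taking the suppressive drug. The general 3-week note defers to whatever recovery is required elsewhere, which points to the rows. This largely stands, and it is why the point is minor. It does not repair the text: to reach this rule a site has to disregard the footnote's stated recovery level.

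**Not the only mismatch.** The footnote is the only rule in 8.3 that names baseline, but a reader might go on to infer that it is the only stopping level stricter than its restart level. The AST/ALT row is another.

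**Investigator discretion.** The closing bullet of 8.3.4 could be read as letting the principal investigator settle prolonged haematological holds. But it uses a different limit (over 4 weeks) and does not say whether it overrides the footnote.

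**Visit schedule.** Section 9.1 schedules blood counts only on day 1 of each 6-week cycle, so the 3-week point is not a planned visit. Yet ending a hold needs a repeat count in any case. Day 1 of the next cycle is day 43, and its count may be taken up to 7 days earlier (days 36 to 43). It therefore falls 3 weeks after an interruption on days 15 to 22 (36 - 21 = 15; 43 - 21 = 22). The objection lowers the chance of seeing the conflict but does not remove it.

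**Conclusion.** The footnote is wrong as written, and the point is minor. The rows and the footnote give opposite instructions for a patient at grade 2 or better but below baseline at 3 weeks, and no text reconciles them. The mismatch itself rests only on the wording. That patients can fall in the gap rests on the entry limits and on the assumption that grade 2 extends below them.

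The consequence is limited to treatment duration and consistency of toxicity discontinuations. If sites take the footnote as a maximum hold, they would rarely diverge. The number affected cannot be estimated.

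A reader might infer that early withdrawals would distort the primary result, since section 10.1.2 generally requires two cycles for response evaluability. The documents do not support that. They give no rate of grade 3-4 cytopenia and nothing that fixes a size or direction, section 12.1 asks for follow-up to continue after treatment stops, and the error rates in 11.3 do not depend on this rule.

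**What to change.** Reword the asterisk footnote along these lines: *if the neutrophil or platelet count is still worse than grade 2 three weeks after sunitinib was interrupted, the patient comes off protocol therapy.* This makes the stopping level equal the restart level in the four rows. It also matches the general 3-week note in both time limit and consequence, since that note ends protocol therapy, not study participation.

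Add one sentence stating that this 3-week limit, and not the closing bullet of 8.3.4 with its 4-week limit and principal investigator discretion, governs haematological holds. Without it, the 3-week and 4-week limits would still conflict.

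If recovery to baseline is truly intended, change the four grade 3-4 rows of 8.3.3 instead, and say whether baseline means the patient's own count or the baseline grade. The AST/ALT row could be aligned in the same amendment.

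The cost is one footnote and one sentence, or four table rows. No tests, visits or patients are added.
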